9.1 Intercurrent Event Handling Strategy for Estimands

Potential intercurrent events (ICEs) like discontinuing from the treatment may occur. Patients who discontinue from the treatment will be encouraged to stay in the trial after those ICEs and data will be collected through the planned study completion visit.

In general, treatment policy strategy will be used to account for the ICEs for defining estimands corresponding to continuous efficacy endpoints, including the primary efficacy endpoint. All efficacy analyses will be based on the observed data except for categorical efficacy endpoints. For categorical endpoints, composite strategy will be used. For binary responder endpoints, patients whose Week 24 assessment is missing will be considered treatment failures (non-responders). For ordinal response endpoint, missing value at Week 24 will be imputed using the last assessment value available for patients whose Week 24 assessment is missing.

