At the end of the double-masked Treatment Period (Week 24), all patients will be assessed for treatment response: proptosis responders (study eye has >2-mm reduction in proptosis from Baseline without deterioration [ $\geq 2\text{-mm}$  increase in proptosis] in fellow eye) or proptosis non-responders (study eye has <2-mm reduction in proptosis). Proptosis non-responders who have completed the double-masked Treatment Period may choose to receive 8 infusions of TEPEZZA (10 mg/kg for the first infusion and 20 mg/kg for the remaining 7 infusions) in an open-label fashion q3W at Weeks 24, 27, 30, 33, 36, 39, 42 and 45. These patients will return to the clinic at Week 48 for End-of-Treatment assessments, and patients will be contacted by phone/email 30 days after the Week 48 Visit for safety assessment. Proptosis responders, as well as non-responders who choose not to receive TEPEZZA in an open-label fashion, will enter a 30-day Follow-up Period, during which trial drug will not be administered. These patients will be contacted by phone/email 30 days after the Week 24 Visit for safety assessment.

Patients who prematurely discontinue trial drug dosing prior to Week 21 of the double-masked Treatment Period or prior to Week 45 of the open-label Treatment Period will return to the clinic, undergo the scheduled End-of-Treatment assessments (with the exception of the collection of blood samples for biomarker evaluations) and enter the Follow-up Period, provided such continued participation will not detrimentally affect the health, safety and welfare of the patient per Investigator determination. An overview of the trial design is presented in the schematic below, and details of trial activities are provided in [Section 2.1, Schedule of Assessments](#).

Screen	BL	Double-blinded Treatment Period								Open-label Treatment Period 								30-day Follow-up Period 	
		TEPEZZA or Placebo + 24 Weeks								(Proptosis Non-responders who Choose to Receive Open-label TEPEZZA)									
		*	*	*	*	*	*	*	*	*	*	*	*	*	*	*	*	*	
4 weeks pre-dose	Day 0 	W3 	W6	W9	W12	W15	W18	W21	W24 	W27 	W30	W33	W36	W39	W42	W45	W48 		
Randomization  ←————— Trial Week —————→																			
* Infusion of trial drug (TEPEZZA or placebo in double-blinded Treatment Period and open-label TEPEZZA in open-label Treatment Period) BL=Baseline; q3W=once every 3 weeks; W=Week.																			

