#### 9.3.3.1 Discontinuation of Patients from Treatment

The primary reason for discontinuation from trial drug should be recorded on the eCRF using 1 of the following categories:

- AE. The patient experiences an AE that imposes an unacceptable risk to the patient's health, or the patient is unwilling to continue because of an AE. Patients who discontinue trial drug due to an AE will remain in the trial unless they withdraw from the trial for another reason. AEs requiring permanent trial drug discontinuation per the protocol include:
  - A drug-related anaphylactic reaction as defined by Sampson criteria (see Appendix 17.3 for clinical criteria).
  - Diagnosed or suspected inflammatory bowel disease (e.g., diarrhea with or without blood or rectal bleeding associated with abdominal pain or cramping/colic, urgency, tenesmus or incontinence for more than 4 weeks without a confirmed alternative diagnosis OR endoscopic or radiologic evidence of enteritis/colitis without a confirmed alternative diagnosis).
- Lack of Efficacy. Discontinuation of trial drug due to lack of efficacy is at the discretion of the Investigator or patient and may occur if the Investigator determines that trial drug administration is not benefiting the patient. Patients who discontinue trial drug due to

lack of efficacy will remain in the trial unless they withdraw from the trial for another reason.

- Lost to Follow-up. The patient does not return to the clinic for scheduled assessments and does not respond to the site's attempts to contact the patient.
- Withdrawal by Patient/Guardian. The patient wishes to withdraw from trial drug. The clinical site should attempt to determine the underlying reason for the voluntary withdrawal and document it on the eCRF
- Trial Terminated by Sponsor. The Sponsor, IRB or regulatory agency terminates the trial.
- Pregnancy.
- Death.
- Completed. The patient completed treatment.

Patients who prematurely discontinue trial drug prior to Week 21 of the double-masked Treatment Period or who enter the open-label Treatment Period and discontinue trial drug prior to Week 45 of the open-label Treatment Period will return to the clinic, undergo the scheduled End-of-Treatment assessments (with the exception of the **CCI** [REDACTED]

**CCI** [REDACTED] and enter the Follow-up Period. Patients who discontinue due to an AE should be followed until resolution or stabilization of the AE, or an adequate explanation for the event is obtained.

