* Infusion of trial drug (TEPEZZA or placebo in double-masked treatment period and open-label TEPEZZA in open-label treatment period).

BL=Baseline; q3W=once every 3 weeks; W=Week.

1. Patients will be randomized in a 2:1 ratio to receive:
 - a. TEPEZZA (10 mg/kg on Day 1 followed by 20 mg/kg q3W for the remaining 7 infusions); or
 - b. Placebo (placebo q3W for all 8 infusions).
2. Visit windows are ± 3 days for Weeks 3, 6, 9, 12, 15, 18 and 21 of double-masked treatment period and Weeks 27, 30, 33, 36, 39, 42 and 45 of open-label treatment period, and ± 7 days for Week 24 of double-masked treatment period, Week 48 of open-label treatment period and 30-day Follow-up Period.
3. All patients will be contacted by phone/email the day after infusion for the first and second infusions during the double-masked treatment period and during the open-label treatment period, and thereafter as deemed appropriate; additional phone/email contacts will occur the day after any clinic visit where a patient experiences an infusion-related adverse event.
4. Patients who are proptosis non-responders at Week 24 of the double-masked treatment period will be offered the option to receive 8 infusions of TEPEZZA (10 mg/kg on Day 1 followed by 20 mg/kg for the remaining 7 infusions) in an open-label fashion.
5. All patients will be contacted via phone or email 30 days (± 7 days) following the Week 24 (responders and non-responders who choose not to receive open-label TEPEZZA) or Week 48 (non-responders who receive open-label TEPEZZA) Visit.

[figure not shown]

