4.2 Primary Analysis

The primary analysis of efficacy, safety and tolerability is planned after all patients complete the Week 24 visit assessments in the double-masked treatment period or terminate early from the study prior to Week 24. Efficacy analyses are based on data collected from the Screening visit through Week 24 visit. Safety analyses are based on data collected up to last patient’s Week 24 visit date.

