5.4.3 Visit Windows for Analysis

For analyses that present visit-based data, the variables will be summarized based on the scheduled visits with derived analysis visit windows, with the exception of PK data, anti-drug antibody (ADA)/neutralizing antibody (NAb) data, and **CCI** [REDACTED], which will be analyzed based on nominal visits. For the visits on and after the first dose date, the actual visit date will be mapped to the derived analysis visit windows based on the study day.

Visit windows have been constructed so that every observation (unscheduled visits included) collected can be allocated to the scheduled analysis visit for planned analyses. The actual assessment day will be mapped to the windows defined for each scheduled study visit with following rules.

For multiple non-missing continuous measurements:

- If more than 1 assessment falls within a visit window, the closest non-missing valid assessment to the scheduled day will be used in the analysis.
- If 2 non-missing assessment actual dates are equidistant from the target day, the later visit will be used in the analysis.
- If there is more than 1 record on the selected day and the time is not recorded, the average will be taken, unless otherwise specified.
- For retest values of laboratory data, the retest value (the last valid observation assessed on the same visit day) will be chosen.

For multiple non-missing categorical measurements:

- For Baseline, the last available record on or prior to the date of the first dose of study drug will be selected. If there are multiple records with the same time or no time recorded on the same day, the value with the lowest severity will be selected (e.g., normal will be selected over abnormal for hematology).
- For postbaseline visits, if there are multiple records with the same time or no time recorded on the same day, the value with the worst severity within the window will be selected (e.g., abnormal will be selected over normal for hematology).

The Analysis Visit Window for the primary endpoint (change of proptosis), other endpoints (**CCI** [REDACTED]) and exploratory endpoint (**CCI** [REDACTED]) is shown in **Table 1**. The details for the other analysis visit window rules will be included in the TLF shell document.

Table 1 Analysis Visit Windows for Primary Endpoint

Analysis Visit	Target Study Day of Visit	Analysis Visit Window
Baseline	1	Non-missing assessment on or before the first dosing date (randomization)
Week 3	22	Day 2 to 32

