Week 6	43	Day 33 to 64
Week 12	85	Day 65 to 106
Week 18	127	Day 107 to 148
Week 24	169	Day 149 to 179*
Week 27	190	Day 180 to 200
Week 30	211	Day 201 to 232
Week 36	253	Day 233 to 274
Week 42	295	Day 275 to 316
Week 48	337	≥ Day 317

* For patients who did not enter the open-label treatment period, Week 24 analysis visit window is \geq Day 149.

Data from all assessments (scheduled and unscheduled), including multiple assessments, will be included in listings.

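### The SAP promises treatment-policy follow-up of patients who stop drug, but the visit rules give them one undated PW1 proptosis reading and no Week 24 visit

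*SAP*

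**What the plan says.** **The estimand.** SAP 9.1 states that "treatment policy strategy will be used to account for the ICEs" for continuous endpoints, including the primary one, and that these analyses rest on observed data. SAP 9.2 names early treatment discontinuation as the intercurrent event. Patients who stop are "encouraged to stay in the trial after those ICEs and data will be collected through the planned study completion visit".

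**The visits.** The Protocol synopsis (Trial Design) says of patients who stop before Week 21 that, once back at the site, they "undergo the scheduled End-of-Treatment assessments (with the exception of the collection of blood samples for biomarker evaluations) and enter the Follow-up Period". Protocol 9.1 and 9.3.3.1 repeat this. Footnote 3 of the schedule (Protocol 2.1 and SAP 15.1) describes one clinic visit with the W24/PW1 assessments and gives no date for it. Protocol 9.5.1.1 lists PW1 as the alternative to Week 24 for proptosis. Under Protocol 9.5.6.4 the Follow-up Period is a phone or email contact about adverse events and medication.

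**Text pointing the other way.** Protocol 9.3.3.1 says: "Patients who discontinue trial drug due to an AE will remain in the trial unless they withdraw from the trial for another reason". It says the same of stopping for lack of efficacy. It names no later proptosis visit in either case.

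**The analysis rules.** SAP 5.4.3 assigns readings to visits by study day. If several fall in one window, "the closest non-missing valid assessment to the scheduled day will be used in the analysis". "For patients who did not enter the open-label treatment period, Week 24 analysis visit window is" Day 149 or later. SAP 4.2 starts the primary analysis once all patients "complete the Week 24 visit assessments in the double-masked treatment period or terminate early from the study prior to Week 24".

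**The concern.** A treatment-policy estimand needs the outcome at Week 24 whether or not the patient is still on drug. The visit rules appear to end proptosis measurement at PW1, which may come weeks or months before Week 24. SAP 4.2 also leaves unclear where a patient belongs who stopped drug, attended PW1 and moved to Follow-up without leaving the study.

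Without a Week 24 reading, the MMRM predicts that value under missing-at-random, chiefly from readings taken on drug and from patients in the same arm who continued. The result would carry the treatment-policy label while leaning toward the effect had everyone stayed on drug. It would favour TEPEZZA if stoppers have less benefit at Week 24 than continuers.

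**Working it through.** **1. The plan's own figure.** Inputs (SAP 5.1, Protocol 9.6.7): 38 and 19 patients, difference 2.0 mm, SD 2.5 mm, two-sided alpha 0.05.

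- SE = 2.5 × √(1/38 + 1/19) = 0.702 mm.
- 2.0/0.702 − 1.960 = 0.887, which gives power 81.3%. The stated 81% is reproduced.
- The sample-size text has no allowance for discontinuation.

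**2. Can PW1 serve as Week 24?** Nominal doses fall on Days 1, 22, 43, 64, 85, 106 and 127, which are the seven possible last doses before Week 21. Proptosis is scheduled on Days 22, 43, 85 and 127. The SAP Table 1 windows are Week 3, Days 2–32; Week 6, 33–64; Week 12, 65–106; Week 18, 107–148; Week 24, Day 149 or later. The PW1 lag is not stated. The table assumes 21 days, one dosing interval; the last column is 149 minus the last-dose day.

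| Last dose | PW1 day | Analysis visit | PW1 displaced by a reading nearer target? | Lag needed for Week 24 (days) |
|---|---|---|---|---|
| Day 1 | 22 | Week 3 | No | 148 |
| Week 3 | 43 | Week 6 | No | 127 |
| Week 6 | 64 | Week 6 | Yes (Day 43) | 106 |
| Week 9 | 85 | Week 12 | No | 85 |
| Week 12 | 106 | Week 12 | Yes (Day 85) | 64 |
| Week 15 | 127 | Week 18 | No | 43 |
| Week 18 | 148 | Week 18 | Yes (Day 127) | 22 |

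- Lag 1–10 days: 0 of 7 reach Week 24; 4 of 7 are displaced (last dose Week 3, 6, 12 or 18).
- Lag 11–21 days: 0 of 7 reach Week 24; 3 of 7 are displaced.
- Lag 22–42 days: 1 of 7 reaches Week 24 (last dose Week 18).
- Visits may move by ±3 "days for Weeks 3, 6, 9, 12, 15, 18 and 21 of double-masked treatment period" (SAP 3.1). The last three thresholds then become 61–67, 40–46 and 19–25 days.

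**3. Ceiling on the overstatement.** Let q be the share of TEPEZZA patients who stop and f the share of the 2.0-mm effect they lack at Week 24. Both are assumptions. The treatment-policy effect is 2.0 × (1 − qf). A model that predicts stoppers as continuers returns 2.0. The difference is 2qf.

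| q | f | TEPEZZA patients | 2qf (mm) | In units of SE |
|---|---|---|---|---|
| 5% | 25% | 1.9 of 38 | 0.025 | 0.04 |
| 10% | 50% | 3.8 of 38 | 0.10 | 0.14 |
| 20% | 100% | 7.6 of 38 | 0.40 | 0.57 |

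The ceiling could be exceeded only if stoppers did better than average while on drug.

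**4. Allowing for loss already visible in the data.** If stoppers already lag at their last usable reading (week s), the model carries part of that forward. To first order the overstatement is q × (2f − D). D is the mean, over the seven stop points, of the deficit at week s times ρ^((24−s)/6), with ρ the correlation per 6 weeks. With PW1 at 21 days the last usable weeks are 3, 6, 6, 12, 12, 18, 18.

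Example: the benefit was never gained on drug, linear build-up, f = 50%. The deficits at Weeks 3, 6, 12 and 18 are 0.125, 0.25, 0.50 and 0.75 mm.

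- ρ = 0.6: D = (0.021 + 2×0.054 + 2×0.180 + 2×0.450)/7 = 0.198; 0.10 × (1 − 0.198) = 0.080 mm.
- ρ = 0.9: D = (0.086 + 2×0.182 + 2×0.405 + 2×0.675)/7 = 0.373; 0.10 × (1 − 0.373) = 0.063 mm.

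The exact large-sample limit of the likelihood fit (arm-specific visit means, common unstructured covariance, no baseline covariate, stops spread evenly over the seven doses) gives 0.079 and 0.061 mm. Exact ranges over ρ = 0.6 and 0.9 and the shapes tried:

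| Scenario | q = 10%, f = 50% (mm) | q = 20%, f = 100% (mm) |
|---|---|---|
| No loss visible at PW1 | 0.100 | 0.400 |
| Half the loss visible at PW1 | 0.077–0.095 | 0.304–0.377 |
| Benefit never gained on drug (linear or front-loaded) | 0.036–0.079 | 0.137–0.312 |

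**The case against.** **The text may keep Week 24.** Stoppers stay in the trial under Protocol 9.3.3.1. Protocol 9.5.6.2.5 equates Week 24 with End-of-Treatment 1, and Protocol 9.5.6.4 counts the follow-up contact from the Week 24 visit. On this reading the End-of-Treatment assessment happens at calendar Week 24. That is possible, so the loss of data is likely rather than certain. But no section schedules such a visit for stoppers, and the single-visit rule also stands in SAP 15.1, so this is not a mismatch of document versions.

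**The PW1 lag is assumed and could be long.** Protocol 9.4.6.3.2 lets an infusion be skipped, so PW1 could fall 42 days after the last dose. After a last dose at Week 15 that is Day 106 + 42 = 148 on nominal dates, still one day short. Within the ±3-day allowance some such patients would reach Week 24.

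**The effect is small and rests on guesses.** True of the working case, which is at most 5% of the 2-mm effect. Protocol 7.1.2 also reports persistence for about a year off treatment. That points to the lower end, but it comes from active disease and does not settle partial courses in inactive disease.

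**Other handling exists.** Missing Week 24 values count as non-response in the responder analysis, but that is a different endpoint. SAP 9.2.1 imputes zero change only for patients with no post-baseline value. The sensitivity analyses in SAP 9.2.2 are redacted, so nothing is claimed about them; no analysis can supply readings that were not taken.

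**A displaced PW1 holds little off-drug information.** Fair for short lags. The displacement is secondary to the missing Week 24 reading.

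**Conclusion.** The concern holds. The estimand and the statement on data collection in SAP 9.1 do not match the visit rules in either document. Followed as written, those rules are likely to leave most early stoppers without a Week 24 value, so the primary estimate would lie closer to the effect had patients continued than to the declared one. That likelihood rests on PW1 being held within a few weeks of stopping, which the documents do not state.

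The size depends on q and f, for which the documents give no figures. The overstatement is at most 0.025 mm in the low case, 0.10 mm in the working case and 0.40 mm in the extreme case, and less where the loss already shows on drug or at PW1. It is zero if nobody stops or stoppers lack no benefit. This should be fixed: off-drug readings not taken at the time cannot be recovered later.

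**What to change.** **Main option.** Reconcile SAP 9.1, 9.2 and 15.1 with the Protocol synopsis and Protocol 2.1, 9.1, 9.3.3.1, 9.5.1.1 and 9.5.6.4. For patients who stop drug without withdrawing consent, keep the Week 24 proptosis assessment in addition to PW1 and include it in the primary MMRM. State when PW1 takes place, and whether the closest-to-target rule is meant to discard it in favour of an on-drug reading. Make clear in SAP 4.2 that the primary analysis waits for these Week 24 readings.

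The cost is a short amendment and one retained visit for a few patients: about 2 to 8 of 38 on TEPEZZA at the assumed rates of 5% to 20%, plus any on placebo. Some will decline, so some values will still be missing.

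**Fallback if that is not feasible.** Delete the statement that data are collected through study completion, restate the estimand and its missing-at-random assumption, and say how PW1 and later off-drug values are used. This costs SAP wording only, but the primary result then no longer answers the treatment-policy question.

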9.2 Primary Efficacy Endpoint

The primary efficacy endpoint is the change in proptosis from Baseline at Week 24 in the study eye.

Population	ITT Analysis Set defined as all patients who were randomized in the trial
Endpoint	Change from Baseline at Week 24 in proptosis of the study eye
ICE	Discontinued from treatment early
Population-level Summary	Difference (TEPEZZA minus placebo) in least squares means of changes from Baseline at Week 24 in proptosis of the study eye between the treatment groups

9.2.1 Primary Analysis Method

The primary efficacy endpoint analysis will be conducted based on the ITT analysis set.

A Mixed-Model for Repeated-Measures (MMRM) analysis of covariance model fitting to the individual change from Baseline values for the study eye will be used for the analysis of change from Baseline in proptosis. The model includes Baseline value, treatment group, visit, visit-by-

treatment and visit-by-Baseline value as fixed effects, and patient as a random effect as shown below:

$$y_t = X\beta + Z\gamma + \epsilon,$$

where

- y_t is a vector of change in proptosis from Baseline at visit t
- visit t is Week 3, 6, 12, 18 or 24
- β is an unknown vector of fixed-effects parameters with known design matrix X = (Baseline value, treatment group, t , t * treatment group, t * Baseline value)
- γ is an unknown vector of random-effects parameters with known design matrix Z = patient, and
- ϵ is an unknown random error vector.

It is assumed that γ and ϵ are Gaussian random variables that are uncorrelated and have expectations 0 and variances G and R , respectively. The variance of y is

$$V = ZGZ' + R,$$

where G and R are unstructured covariance.

If there are model convergence issues with an unstructured variance-covariance matrix, the following three variance-covariance matrices will be attempted in order until one converges: heterogeneous Toeplitz (TOEPH), heterogeneous compound symmetry (CSH), and Toeplitz (TOEP). If there are any patients in the ITT analysis set without post-baseline values, a change from Baseline value of 0 will be imputed at the first post-baseline visit (in order to avoid exclusion of these patients from the MMRM analysis).

The p-values for all terms in the model will be presented, as well as the overall treatment group least squares (LS) means and associated standard errors (SE), and their difference, SE of the difference, 95% confidence intervals (CIs) for the difference and p-value. The primary analysis will be to test the treatment difference at Week 24. Analysis results at Week 24 present the estimated LS means, SEs and their difference with the SE, 95% CI for the difference and p-value.

Further, the analysis will be repeated using assessments obtained from the fellow eye based on the ITT analysis set.

Descriptive summaries of change from Baseline in the proptosis for study eye and fellow eye at each scheduled visit will be provided by treatment group for each treatment period based on the ITT analysis set.

Changes from Baseline in proptosis of the study eye over time during the double-masked treatment period will be depicted by treatment group using LS means of change and corresponding 95% CI.

9.2.2 Sensitivity Analysis Method

CCI

